Participants randomised to control will receive no interventions and will be requested to maintain their habitual lifestyle during the six week intervention phase. Ahead of week five, participants will be posted a wrist worn physical activity monitor to wear continuously for the final two weeks of the study.

Participants will also complete a food diary during this time (two week and one weekend day in week five and six).

Participants randomised to the exercise training intervention will complete 24 moderate-intensity exercise training sessions over the subsequent six weeks (four times per week; ~50 min per session). Each week, at least one of the four exercise training sessions will be supervised by the research team. The remainder of the sessions each week will be unsupervised but monitored objectively using a heart rate monitor. Post- intervention assessments will be completed 48 h - 72 h after the final exercise training session.

After the intervention phase, participants will attend two final assessment sessions to obtain post-intervention data. Assessment visit three will be a repeat of assessment visit one whilst assessment visit four will be a repeat of assessment visit two (minus the medical examination).

[figure not shown]

Figure 1: flow diagram of the study protocol
 SPMIC – Sir Peter Mansfield Imaging Centre; QMC – Queens Medical Centre, Nottingham; LDC – Leicester Diabetes Centre; LU – Loughborough University

Primary and secondary endpoints / outcome measures

Co-primary outcomes: Liver saturated lipid index (%) determined by proton magnetic resonance spectroscopy (¹H-MRS) using a 3T MRI scanner

- 1) Comparison between obese men with NAFLD versus obese men with NAFLD and T2DM (Part A)
- 2) Response to the six week exercise training intervention (Part B)

Secondary outcomes:

- Liver unsaturated lipid index (%) - measured using ¹H-MRS
- Liver polyunsaturated lipid index (%) - measured using ¹H-MRS
- Total hepatic lipid composition (%) - measured using ¹H-MRS
- Liver inflammation - measured using MRI
- Visceral adipose tissue - measured using MRI
- Subcutaneous abdominal adipose tissue - measured using MRI
- Body mass and body fat percentage
- Blood pressure
- Aerobic fitness (peak oxygen uptake)
- Circulating metabolic biomarkers (fasted blood sample)
 - Liver enzymes
 - Glucose
 - Insulin
 - Lipids
 - HbA1c
 - HOMA-IR (surrogate marker of peripheral insulin resistance)
 - ADIPO-IR (surrogate marker of adipose tissue insulin resistance)

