14. STATISTICS

Description of statistical methods

Descriptive statistics will be calculated to outline the characteristics of the study sample. Normality of data will be assessed using histograms and box plots, while further analysis of skewness and kurtosis will be conducted if normality is not clear from the histograms and box plots. Depending on the distribution of data, participant characteristics will be reported as mean (SD) or median (IQR) and number (percentage) for continuous variables and for categorical variables respectively.

For part A of the study, data will be checked for parametric assumptions. Independent samples t-tests will be used to analyse differences in continuous variables between study groups (obese men with NAFLD and obese men with NAFLD and T2DM in part A of the study). To examine factors associated with NAFLD and T2DM, univariate logistic regression models will be performed with NAFLD and T2DM (diabetic individuals with NAFLD vs. non-diabetic individuals with NAFLD) as the dependent variable. All variables significantly associated with NAFLD and T2DM in univariate logistic regression analyses will be included in multivariate logistic regression analysis.

For part B of the study, baseline descriptive statistics will be summarised by treatment arm (Intervention vs control). Data will be checked for parametric assumptions. For the primary outcome, change in hepatic saturated lipid index (%) from baseline to six weeks due to moderate-intensity exercise training in men with NAFLD and T2DM/prediabetes, treatment arms will be compared using linear regression modelling. The analysis will include a binary indicator for randomisation group as the explanatory variable, terms for the stratification category (ethnicity) and adjustments for the baseline measure of the outcome (hepatic saturated lipid index).

Complete case analysis will be utilised for the primary analysis. Intention to treat will be carried out as sensitivity analysis, using multiple imputation for missing values. Secondary outcomes will be analysed using similar methods as the main analysis, with an appropriate model selected dependent on the distribution of the outcome.

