The assumptions associated with each model will be assessed and where these are not met alternative models or parameterisations will be considered. A value of $P < 0.05$ will be considered statistically significant for all analyses. Statistical analyses of the baseline data and all future analysis will be carried out using STATA version 15.

The Number of Participants

The sample size for the research outlined in this protocol was undertaken by a statistician in the Leicester Clinical Trials Unit. The sample size calculations were informed by data published in a previous study which validated the method for measuring hepatic fat quality via ¹H-MRS[16].

Part A of this research (cross-sectional analyses) was powered (80%) to detect a difference in the liver saturated fat indices of 0.5 between men with NAFLD with T2DM versus non-diabetic men with NAFLD (alpha 5%, SD 0.4 in each group). 28 participants are needed to provide adequate statistical power for this analysis (14 in each group). Based on the same data, the power calculation showed that 24 participants are needed for Part B of the outlined research (RCT). This is inflated to 26 to allow for expected drop-out (10%).

Please note that the baseline data for all participants entering Part B of this research will be used in Part A and therefore the cross-sectional analyses will include data from 26 men with NAFLD & T2DM and 14 non-diabetic men with NAFLD.

Procedure for dealing with missing and spurious data

Missing data will be replaced using multiple imputation or another appropriate method. In Part B, participants completing less than 85% of all training sessions will not be included in the final analysis.

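### Part A names an independent-samples t-test for 26 v 14 men without stating its form; fixing the Welch form in advance removes an avoidable dependence on equal SDs (minor)

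*Protocol*

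**What the plan says.** Section 14 (Description of statistical methods) gives the Part A analysis in one sentence: "Independent samples t-tests will be used to analyse differences in continuous variables between study groups". Just before it stands a general check: "For part A of the study, data will be checked for parametric assumptions". A later sentence in the same section supplies the fallback: "The assumptions associated with each model will be assessed and where these are not met alternative models or parameterisations will be considered". No alternative is named, and no variance check is described. The only diagnostics listed are for normality: histograms, box plots, skewness and kurtosis.

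Section 9 makes the Part A comparison of the liver saturated lipid index one of two co-primary outcomes. Under The Number of Participants in section 14, Part A "was powered (80%) to detect a difference in the liver saturated fat indices of 0.5" with "alpha 5%, SD 0.4 in each group", giving 28 men, 14 in each group. The same subsection then says that "the cross-sectional analyses will include data from 26 men with NAFLD & T2DM and 14 non-diabetic men with NAFLD". A P value below 0.05 "will be considered statistically significant for all analyses".

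The terms equal-variance, pooled and Welch do not appear in the protocol.

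**The concern.** The pooled t-test tolerates unequal SDs when the groups are of similar size. It does not when one group is nearly twice the other (26/14 = 1.86). The pooled variance is then weighted towards the larger group, while the true variance of the difference is dominated by the smaller one. If the larger group is the more variable, the standard error is too big and power is lost. If the smaller group is, the standard error is too small and false positives rise.

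The planning calculation assumed equal groups, where this hardly matters. The analysed comparison is unbalanced, and the analysis text does not take that up. At stake are the P value and confidence interval of a co-primary comparison and of any other Part A outcome analysed by t-test. As written, the choice between the two forms can also be made after the data have been seen.

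**Working it through.** **Inputs.** From section 14: difference 0.5, SD 0.4 in each group, alpha 5%, power 80%, planned 14 v 14, analysed 26 v 14. Assumed here: a two-sided test (sidedness is not stated), normal data, and SD ratios up to 2 in either direction (no group-specific SDs are given).

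**1. The plan's own figure.** The normal approximation gives n per group = 2 × (1.96 + 0.84)² × (0.4/0.5)² = 2 × 7.85 × 0.64 ≈ 10.05, so 11. Exact t power is 79.6% at 11 per group and 83.3% at 12, so 12 per group (24 in total) meets 80%. The stated 14 per group gives 88.9%. The figure of 28 is therefore not reproduced from its stated inputs, but it errs on the safe side.

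**2. Power at the sizes analysed, equal SDs.** Noncentrality = 0.5 / [0.4 × √(1/14 + 1/26)] = 0.5 / (0.4 × 0.3315) = 3.77 on 38 df. This gives 95.7% power for the pooled test.

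**3. Why imbalance matters.** Write s₁ for the SD of the 14 and s₂ for the SD of the 26.
- Variance the pooled test uses, on average: [(13s₁² + 25s₂²)/38] × (1/14 + 1/26).
- True variance: s₁²/14 + s₂²/26.
- s₁ = 0.6, s₂ = 0.4: 0.2284 × 0.1099 = 0.0251 against 0.0319. Ratio 0.79, so the standard error is about 11% too small.
- s₁ = 0.4, s₂ = 0.6: 0.2916 × 0.1099 = 0.0320 against 0.0253. Ratio 1.27, so the standard error is about 13% too large.
- At 14 v 14 the two expressions are identical for any SDs.

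**4. Size of the effect.** Simulation, 400,000 replicates per setting, 14 v 26, two-sided 5%:

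| SD of 14 / SD of 26 | Type I error, pooled | Type I error, Welch | Power at 0.5, pooled | Power at 0.5, Welch |
|---|---|---|---|---|
| 0.4 / 0.4 (planned) | 5.0% | 4.9% | 95.7% | 95.2% |
| 0.4 / 0.5 | 3.7% | 5.0% | 89.5% | 91.6% |
| 0.4 / 0.6 | 2.9% | 5.0% | 80.2% | 86.4% |
| 0.4 / 0.8 | 2.1% | 5.0% | 58.3% | 72.8% |
| 0.5 / 0.4 | 6.6% | 5.0% | 90.6% | 86.8% |
| 0.6 / 0.4 | 8.2% | 5.1% | 84.0% | 75.7% |
| 0.8 / 0.4 | 10.5% | 5.1% | 69.8% | 54.3% |

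In the last three rows the pooled test's apparent power advantage comes from its inflated error rate. At 14 v 14 the pooled error stayed at 5.0% to 5.3% for SD ratios of 1, 1.5 and 2, so the exposure comes from the 26:14 split.

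**5. Does an assumption check repair it?** The protocol names no variance check, so a 5% F-test of variances that switches to Welch was taken as an example:

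| SD of 14 / SD of 26 | Check triggers | Resulting type I error |
|---|---|---|
| 0.6 / 0.4 | 40% | 6.5% |
| 0.8 / 0.4 | 82% | 5.8% |
| 0.4 / 0.6 | 33% | 4.0% |
| 0.4 / 0.8 | 77% | 4.5% |

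The check helps, but it usually misses a 1.5-fold ratio at these sample sizes and leaves the error at about 4% to 6.5%.

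**6. Cost of Welch when SDs are equal.** 95.7% v 95.2% at a difference of 0.5, and 79.8% v 78.8% at 0.38: about 0.5 to 1 point.

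**The case against.** The strongest reply is that nothing in the protocol is wrong. Welch's test is also an independent-samples t-test, so the text is compatible with the fix. The choice of form is often left to the SAP, which is not shown. The assumption check and the fallback clause give room to change method. The only SDs in the document are equal, and under them the two forms can hardly be told apart. Every figure showing harm rests on an assumed SD ratio.

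Most of this stands, and it rules out three stronger readings that a reader might infer.

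- **That the protocol prescribes the equal-variance test.** It does not. The common SD of 0.4 is a planning assumption for sample size, not an analysis specification.
- **That false positives of 8% to 10% are to be expected.** That needs the 14 men with HbA1c below 6% to be the more variable group, and nothing in the protocol suggests this. The wider HbA1c range of the other group (6.0% to 10%) is not evidence about the SD of the liver saturated lipid index. If it pointed anywhere, it would be towards a conservative test with less power. At SDs of 0.6 and 0.4 that test still reaches the planned 80%.
- **That every Part A secondary outcome is affected.** Section 14 also provides that the model for secondary outcomes depends on their distribution.

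The reply does not remove the remaining point. The protocol itself sets an unbalanced co-primary comparison, names a test without its form, and leaves any change to a check whose criterion and consequence are open. A check-then-switch rule is also a weaker safeguard than choosing the robust form at the outset.

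**Conclusion.** The point holds as a minor, cheap improvement. Section 14 leaves the form of the t-test open for a comparison that is 26 v 14 by design. If the conventional pooled form is used, its error rate depends on equal SDs: about 2% to 10.5% over SD ratios up to 2 in either direction, against about 5% for Welch throughout. A variance pre-test narrows the range to about 4% to 6.5% but does not close it.

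This rests on normal data, a two-sided test and an assumed range of SD ratios. The direction and size in this trial cannot be known from the protocol. At the planned SDs there is no material difference: 5% error and about 95% power with either form.

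**What to change.** In section 14, name the unequal-variance (Welch) t-test as the Part A default for outcomes analysed by t-test, and state that this does not depend on a preliminary variance check. The existing assumption clause can stay for other departures, such as marked skewness. If an SAP exists, it should carry the same wording.

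The cost is one phrase in the protocol and one option in the planned software. No change to sample size is needed. If the SDs turn out equal, about 0.5 to 1 percentage point of power is given up.

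A linear regression of the index on group with heteroscedasticity-robust, small-sample standard errors would be an acceptable alternative.

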Participants will be asked to attend the second study assessment visit having not eaten since the prior evening. These visits will therefore occur in the morning (before 10:30). At the start of this visit participants will provide a fasting venepuncture blood sample (50 mL blood) after having sat down for 10 minutes. This sample will be collected from an antecubital vein by an individual trained and experienced in phlebotomy. One blood bottle will be sent to hospital pathology labs for the analysis of glycated haemoglobin. The remaining samples will be processed immediately and stored until the end of the trial within -80°C freezers at the research sites. Following the last participants visit, samples will

be transported to Loughborough University (at -80°C) by a commercial courier. Samples will then be analysed in batch for:

- Lipids
- C-reactive protein
- Liver enzymes
- Glucose
- Insulin
- Nonesterified fatty acids
- Hepatokines
- Inflammatory proteins
- Genotype (gene variants linked to NAFLD)

Medical evaluation and aerobic fitness

A healthcare professional will take a full medical history from participants in order to identify any factors that may prohibit individuals from completing the study. Blood pressure will be measured, and a 12 lead ECG and a physical examination* will also be performed. Finally, a symptom limited progressive treadmill exercise test will be undertaken on a treadmill. This test will require participants to exercise at increasingly harder intensities until volitional exhaustion. A clinical professional will monitor participants' blood pressure and ECG during this test which will be terminated if clinically indicated.

* The physical examination is optional and dependent on findings from Medical History and 12 Lead ECG. It is to be performed by individuals qualified to do physical examinations.

Randomisation

After visit two, participants entering Part B of the study will be randomised (1:1) to condition (exercise training or control). Randomisation will be performed by the trial statistician ([name]) (see section 13 for additional details). The involvement of participants who are only completing Part A of the study will end at this point.

Six week intervention

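### Part B's allowance from 24 to 26 men counts drop-out only, although the protocol also removes exercise-arm men below 85% attendance; and 26 covers 7.7% loss, not 10%

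*Protocol*

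**What the plan says.** Three statements in Protocol section 14 bear on how many men reach the Part B primary analysis.

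- **The Number of Participants.** For Part B, "the power calculation showed that 24 participants are needed for Part B of the outlined research (RCT"). The next sentence reads "This is inflated to 26 to allow for expected drop-out (10"%). Drop-out is the only loss named, and the term is not defined.
- **Procedure for dealing with missing and spurious data.** In Part B, "participants completing less than 85% of all training sessions will not be included in the final analysis".
- **Description of statistical methods.** "Complete case analysis will be utilised for the primary analysis". Intention to treat with multiple imputation is the sensitivity analysis.

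Section 11 (Randomisation) says that "participants entering Part B of the study will be randomised (1:1) to condition (exercise training or control"), and the study summary in section 3 gives 13 men per group. Sections 9 and 12 set the exercise programme at 24 sessions over six weeks.

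Power, difference, SD and alpha are printed for Part A: it "was powered (80%) to detect a difference in the liver saturated fat indices of 0.5", with "alpha 5%, SD 0.4 in each group". Part B is tied to these only by the words "Based on the same data, the power calculation showed that 24 participants are needed".

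**The concern.** The inflation is meant to ensure that enough men are left in the analysis. It counts one route out, while the protocol creates two. A man can attend every assessment visit, have a usable post-intervention scan and still be left out because he completed too few sessions. He has not dropped out in the ordinary sense, so the 10% does not obviously cover him. Controls have no sessions to miss, so this loss falls on the exercise arm alone and unbalances the groups, which costs slightly more power than the same loss spread over both.

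Because the primary analysis uses complete cases, each man lost by either route reduces the analysed number. At stake is whether the stated sample size describes the analysis that will be done. The drop-out arithmetic is also slightly off, but that is secondary.

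**Working it through.** **Inputs.** Required 24, recruited 26, drop-out 10%, adherence threshold 85% (all section 14); 24 sessions (sections 9 and 12); 1:1 allocation, 13 per group (sections 11 and 3). For power: difference 0.5, SD 0.4, alpha 5%, printed for Part A. *Assumptions:* these carry over to Part B, the test is two-sided (the protocol does not say), and the comparison is an unadjusted two-sample t-test.

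**Step 1: reproduce the 24.** The standardised difference is 0.5/0.4 = 1.25. With n1 and n2 men analysed, the noncentrality is 1.25/√(1/n1 + 1/n2) on n1 + n2 − 2 degrees of freedom.

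- 11 v 11: 79.6%
- 12 v 12: 83.3%

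The smallest equal-arm design reaching 80% is 12 per arm, 24 in all. The protocol's figure is reproduced, which supports carrying the Part A inputs over.

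**Step 2: the inflation to 26.**

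- 24 × 1.1 = 26.4, which rounds to 26. This is probably where 26 comes from.
- 24/0.9 = 26.7, so 27, or 28 with equal arms, is what 10% drop-out requires.
- 26 × 0.9 = 23.4 men expected to remain.
- 26 − 24 = 2 losses, and 2/26 = 7.7%.

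**Step 3: the second exit.** 0.85 × 24 = 20.4 sessions, so a man needs 21 to be analysed and is left out with 20 or fewer.

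**Step 4: power as exercise-arm men are lost.** Same formula, control v exercise:

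| Analysed | Total | Power |
|---|---|---|
| 12 v 12 | 24 | 83.3% |
| 12 v 11 | 23 | 81.5% |
| 12 v 10 | 22 | 79.3% |
| 12 v 9 | 21 | 76.7% |

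The 12 v 11 row is about what 10% drop-out leaves. The next two rows add one and two adherence exclusions.

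**Step 5: the same as a rate.** The protocol gives no adherence rate. Let q be the *assumed* share of exercise-arm men who do not drop out but fall below 85%. With 10% drop-out in each arm, 13 × 0.9 = 11.7 controls and 11.7 × (1 − q) exercise men are expected in the analysis.

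| q | Exercise | Total | Power |
|---|---|---|---|
| 5% | 11.1 | 22.8 | 81.2% |
| 10% | 10.5 | 22.2 | 80.0% |
| 20% | 9.4 | 21.1 | 77.2% |
| 30% | 8.2 | 19.9 | 73.7% |

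Power passes below 80% at a q of roughly 10%.

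**The case against.** **The drop-out shortfall is rounding.** Adding 10% to 24 gives 26.4, and the gap from 26 to 26.7 is less than one man. With 23 analysed, power is still 81.5%. This stands, and it is why the point is minor. A reader might infer that the trial is underpowered at its own stated drop-out rate; the figures do not support that.

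**The Part B inputs are inferred.** The 80%, 0.5 and 0.4 are printed for Part A, where 14 v 14 gives 88.9% on those same inputs, so they do not reproduce the Part A number as a minimum. They do reproduce 24 for Part B, but the carry-over remains an assumption. A reader might say that a stated 80% power for Part B is not kept; the protocol states no such figure for Part B.

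**The planned analysis is not an unadjusted t-test.** Section 14 specifies linear regression adjusted for the baseline index and ethnicity. If SD 0.4 is the unadjusted outcome SD and two degrees of freedom go to covariates, a baseline correlation of roughly 0.2 brings 12 v 10 back to 80%, and roughly 0.3 does so for 12 v 9. The protocol gives no correlation, so the gain cannot be computed, but a loss of 0.7 points at 12 v 10 could easily be made up. This stands.

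**The two exits overlap.** A man who withdraws during the six weeks will often also have missed too many sessions, and he is lost only once. Only men who stay and fall below the threshold are additional; q above is defined that way. Drop-out is undefined, so the sponsor could reply that the 10% was meant to include non-adherers. The text does not say so, and even then 26 × 0.9 is below 24.

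**Conclusion.** The sample-size statement is wrong as written, with small consequences. What holds firmly is that the allowance names drop-out alone, while the same section removes a second group of men, in one arm only, with nothing allowed for them. It also holds that 26 covers two losses (7.7%) rather than 10%.

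The effect on power is modest and conditional. If Part A's inputs apply, with a two-sided 5% test and no adjustment, 10% drop-out alone leaves about 81%. One further exercise-arm exclusion gives 79.3% and two give 76.7%. Baseline adjustment may offset some or all of this. How many such exclusions will occur cannot be known from the protocol, so it cannot be said that power will fall below 80%, only that it may.

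Whether the adherence exclusion is itself sound is a separate question and is not judged here. If the rule were removed from the primary analysis, the main part of this point would fall away and only the rounding would remain.

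**What to change.** Reword the inflation sentence in section 14, The Number of Participants, to say that:

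- 26 men cover two losses (7.7%);
- at 10% drop-out about 23 men are analysed, with about 81% power on the assumed inputs, which should be stated as applying to Part B;
- exclusions under the 85% attendance rule are not covered by this allowance. For as long as that rule stands, give the analysed number and power over an assumed range of such exclusions, for example zero to two further exercise-arm men (81.5%, 79.3%, 76.7%).

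If the 10% was meant to include non-adherers, say so and define drop-out accordingly.

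The cost is protocol wording and a slightly less favourable stated figure. No extra patients are needed, and the design and analysis do not change.
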